The proportion of patients who were alive without new/worsening complication at the end of study for artesunate was 0.679 in SEQUAMAT and 0.791 in AQUAMAT (private communication). Therefore, it is estimated that the proportion of patients meeting the proposed clinical endpoint is about 0.75 in the artesunate arm. To date, cipargamin has not been tested in patients with severe malaria. It is assumed that the proportion in the cipargamin regimen would be same as that of artesunate.

From [Figure 3-2](#), a sample size of $n=107$ per regimen is required in order to have at least 80% probability that the half width of 2-sided 90% CIs for the difference between 2 proportions is at most 0.1 if the true proportion is 0.75 for both treatment groups. As patients treated with the same treatment from all cohorts will be pooled together for the analysis using the FAS, this sample size is considered for the artesunate and the cipargamin dose regimen that is used in all cohorts.

Taking account that about 8% patients may be excluded from the FAS, patients from all cohorts will be randomized to yield about 116 randomized each for the artesunate and the cipargamin dose regimen that is used in all cohorts so that 107 patients per group are evaluable for this analysis. The enrollment may be increased if the number of patients excluded from the FAS is higher. Considering the required sample size for each cohort for the primary endpoint (see [Section 3.1](#)) and the potential patient population available for recruitment, the 116 randomized for a treatment group will split into 6 patients for Cohort 1, 14 patients for Cohort 2, 38 patients for Cohorts 3 and 4, and 20 patients for Cohort 5.

Figure 3-2 Plot of probability that half width of 2-sided 90% CIs for 2 proportion difference is at most 0.1 for various true equal proportions

Generated using R 3.4.3.

Safety events

[figure not shown]
Safety events will be evaluated using the safety set, which is expected to be similar to the randomized set. Occurrence of a safety event for a regimen (cipargamin or artesunate) will be evaluated by cohort and overall with all patients pooled from all cohorts. The probability of observing selected minimal number of events is displayed in [Figure 3-3](#) by sample size. From this plot,

- for a treatment group in a cohort with 6 patients, the probability of observing at least 2 events is $> 75\%$ if true event rate is $\geq 40\%$ but $< 20\%$ if true event rate is $\leq 10\%$

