It has been observed in the Phase II study of oral KAE609 formulation for uncomplicated malaria that the most patients have achieved parasite clearance by 24 hours. This implies that post 24 hours results may be negative for all KAE609 patients, which results into a constant value for all the patients. For artesunate, the median parasite clearance time is expected to be >40 hours. Therefore, post 48 hours, results may be negative for all artesunate patients, which results into a constant value for all the patients. In such cases, variables with constant value will be dropped from imputation model, otherwise, SAS procedure, PROC MI will fail with error.

Clinical success at different visits will be imputed using discriminant function by FCS method. The imputations will be done separately for each treatment group. The number of imputations will be set to 100; the seed for the random function will be set to 60912201 for this study.

To generate the multiple imputed data sets, the SAS procedure MI can be used as follows:

The input data set <CLNSUC_dd> should have one record per patient with country, age, baseline weight, gender, log (parasite counts) from baseline up to 18 hours for KAE (and up to 48 hours for artesunate), parasitaemia status from 24 to 72 hours (presence/absence) for each visit for KAE609 (72 hours for artesunate), altered consciousness (yes/no) at each visit, renal impairment (yes/no) at each visit, acidosis (yes/no) at each visit, and clinical success (yes/no) at each visit.

Two outputs will be prepared displaying i) the missing data patterns and the group means as stored in the data set msgpat and ii) the variance information and estimated means with confidence interval and range based on data sets varinfo and param which need to be merged by <treatment group> and <variable>.

The imputed data are saved in data set <impdata>.

For each of the completed dataset, clinical success will be derived according the definition in [Section 2.1.1](#). The percentage of patients with clinical success (\hat{P}) at different timepoints such as 24 hours, 48 hours, 72 hours, hospital discharge, Day 6, Day 8, Day 15, Day 22, and Day 29 will be calculated as $n/N \times 100\%$ for each treatment group and for each of the complete datasets; where n =no. of patients with clinical success and N =no. of patients in FAS.

Combining clinical success rates and 90%CI for each treatment group

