Results from the imputation model will be used to estimate the combined clinical success rates and associated 90%CIs.

[Rubin \(1987\)](#) presented rules how to combine the multiple sets of estimates to produce overall estimates and confidence intervals that adequately incorporate missing data uncertainty.

Following this, average estimate of clinical success rate (P) from m completed datasets will be calculated as $\bar{P}_m = \frac{\sum \hat{P}_i}{m}$, where \hat{P}_i is the estimate of P from i^{th} completed dataset.

Estimate of the pooled variance of the m completed dataset is $T_m = \left(1 + \frac{1}{m}\right) B_m + \overline{U}_m$, where $B_m = \frac{\sum (\hat{P}_i - \overline{P}_m)^2}{m-1}$ (between variance) and $\overline{U}_m = \frac{\sum \hat{U}_i}{m}$ (within imputation variance), $\hat{U}_i = \frac{\hat{P}_i(1-\hat{P}_i)}{n}$. 90% CI for the P will be derived based on Wilson uncorrected method using multiple imputed datasets (MI-Wilson) described by Anne, as follows.

Let t be the quantile of the t_v distribution with the confidence level $1-\alpha$ such that

$$P\left(-t \leq \frac{\overline{P}_m - \overline{P}_m}{\sqrt{T_m}} \leq t\right) = 1-\alpha \text{Eq (1),}$$

where $v = (m-1)\left(1 + \frac{1}{r_m}\right)^2$, and $r_m = \left(1 + \frac{1}{m}\right) B_m / \overline{U}_m$

Substituting the expression for T_m and squaring the terms inside the above probability expression of equation (1) will lead the quadratic equation for P. Solving the quadratic equation for P, two limits (MI-Wilson) will be obtained as follows.

$$\frac{2\overline{P}_m + \frac{t^2}{n} + \frac{t^2 r_m}{n}}{2\left(1 + \frac{t^2}{n} + \frac{t^2 r_m}{n}\right)} \pm \text{sqrt}\left[\frac{\left(2\overline{P}_m + \frac{t^2}{n} + \frac{t^2 r_m}{n}\right)^2}{4\left(1 + \frac{t^2}{n} + \frac{t^2 r_m}{n}\right)^2} - \frac{\overline{P}_m^2}{1 + \frac{t^2}{n} + \frac{t^2 r_m}{n}}\right] \text{Eq (2)}$$

It may be possible that $B_m = 0$ or $B_m = \overline{U}_m = 0$ leading r_m to be undefined. In this case set $r_m = 0$ with $v=\infty$ ([Anne, Jerome 2018](#)). Note: a t-distribution with ∞ degree of freedom is the standard normal distribution.

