As the MIANALYZE procedure expects the parameter estimate in the variables ESTIMATE, and the corresponding standard error in the variable STDERR whereas the MI-Wilson procedure works on solving quadratic equation, MIANALYZE procedure can not be used to combine the 90% CIs for multiple imputations, however, it can still be used to obtain the combined point estimate, \overline{P}_m . For 90% CIs, equation (2) will be used.

Between treatment difference and 90% CI in combined clinical success rates based on MI

After obtaining the individual estimates of clinical success rates and the 90% CIs for each treatment group, the between treatment difference and the corresponding 90% CI for the difference will be calculated as described in [Newcombe 1998](#).

Let \overline{P}_{m1} and \overline{P}_{m2} be the average estimate of clinical success rates, L_{m1} and L_{m2} be the lower confidence limits, and U_{m1} and U_{m2} be the upper confidence limits based on the multiple imputed datasets for the test group and control group, respectively,

Then the Newcombe confidence limits for the difference in clinical success rates, $D_m = \overline{P}_{m1} - \overline{P}_{m2}$ is

$$D_{mL} = D_m - \sqrt{(\overline{P}_{m1} - L_{m1})^2 + (U_{m2} - \overline{P}_{m2})^2}$$

$$D_{mU} = D_m + \sqrt{(U_{m1} - \overline{P}_{m1})^2 + (\overline{P}_{m2} - L_{m2})^2}$$

Example SAS code

#Note: The following codes is written to impute clinical success at hours 24, 48, 72, Days 6, 8, 15, 22 and Day 29 for KAE609.

#Since hospital discharge is at different timepoint for different patients, its not considered for the imputation since its not feasible to provide the fixed number of covariates for imputation of clinical success at discharge.

In general, these items are missing altogether if a patient misses a visit. If a patient does not miss a visit, missing individual item should be minimal.

The following are the convention for variable naming:

- Suffix after '_' indicates timing, ||B= means baseline, H36 means 36 hours posting dosing, D15 means at Day 15, etc.
- Prefix 'par': means dichotomous parasite count (absent or presence)
- Prefix ||ln=: means log parasite count (continuous)
- Prefix ||CLSUC=: means clinical success (yes or no)
- Prefix ||REN=: means renal impairment (yes/no)
- Prefix ||ACID=: means acidosis (yes/no)
- Prefix ||ALTCON=: means altered consciousness (yes/no)

```
ODS LISTING CLOSE;
```

```
ODS OUTPUT MissPattern=msgpat VarianceInfo=varinfo
```

```

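### SAP 5.8.4 divides the multiple-imputation interval by n, which it has just defined as the number of successes; coded as written, the 90% limits are too wide

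*SAP*

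**What the plan says.** SAP 5.8.4 sets out the multiple-imputation sensitivity analysis for clinical success. For each completed data set, the success rate in an arm is n/N × 100%, "where n =no. of patients with clinical success and N =no. of patients in FAS". On the number of completed data sets: "The number of imputations will be set to 100".

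The subsection on combining success rates follows directly. It gives the within-imputation variance as U_i = P_i(1 − P_i)/n and then says: "90% CI for the P will be derived based on Wilson uncorrected method using multiple imputed datasets". The limits are the roots of a quadratic, printed as equation (2), in which every t² term is divided by n. The capital N does not appear there, and n is not given a new meaning.

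The SAP explains that the SAS combining procedure can supply the pooled point estimate but not these limits: "For 90% CIs, equation (2) will be used". The limits for the two arms then enter a Newcombe interval for the treatment difference.

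**The concern.** The definition of n nearest to equation (2) is a count of successes. In a Wilson interval the divisor is the number of patients observed. With the smaller count in its place, the variance is overstated whenever the success rate is below 1, and more so the lower the rate.

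Because equation (2) is to be programmed by hand, no procedure default would put this right. If it were coded as printed, the sensitivity analysis would look less precise than the data allow. A reader comparing it with the main result could then attribute the extra width to missing data when it came from the formula.

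**Working it through.** **Inputs.**
- n = successes and N = FAS patients; U_i and equation (2) as printed: SAP 5.8.4.
- Planning success rate 0.75 in both groups and 107 evaluable patients per group: SAP 3.2.
- Two-sided 90% level, so t = 1.645 and t² = 2.706 when the between-imputation variance is zero (r_m = 0).
- Success rates other than 0.75 are assumptions; the documents give no rate by visit.

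**The SAP's own figure.** SAP 5.8.4 states no numerical result for this interval. The nearest checkable figure is the 107 per group in SAP 3.2. It is meant to give at least 80% probability that the 90% Wilson-uncorrected half-width for a difference is at most 0.1 when both rates are 0.75. Exact enumeration over two binomial arms gives 0.790 at 106 and 0.838 at 107, so 107 is reproduced. In that calculation n means patients.

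**What equation (2) requires.** Setting the squared standardised difference equal to t² gives

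(P̄ − P)² = t²(1 + r)·P(1 − P)/size.

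With a = t²(1 + r)/size, the roots are

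(2P̄ + a)/[2(1 + a)] ± √{ (2P̄ + a)²/[4(1 + a)²] − P̄²/(1 + a) }.

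This is equation (2) term by term, with n standing for size. It is a Wilson inversion only if size is the number of patients.

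**Effect of using successes.** With n = N·P, U = P(1 − P)/(N·P) = (1 − P)/N instead of P(1 − P)/N. The variance is multiplied by 1/P and the width by roughly 1/√P.

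**Numbers at P = 0.75, N = 107, r = 0.** The half-width simplifies to √[a·P(1 − P) + a²/4]/(1 + a).
- Patients: a = 2.706/107 = 0.02529. Half-width = √(0.004742 + 0.000160)/1.02529 = 0.0683.
- Successes: n = 107 × 0.75 = 80.25, a = 0.03372. Half-width = √(0.006322 + 0.000284)/1.03372 = 0.0786.
- Ratio 0.0786/0.0683 = 1.15.

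| N | P | Half-width, patients | Half-width, successes | Ratio |
|---|---|---|---|---|
| 107 | 0.75 (SAP) | 0.068 | 0.079 | 1.15 |
| 107 | 0.50 (assumed) | 0.079 | 0.110 | 1.40 |
| 107 | 0.90 (assumed) | 0.048 | 0.051 | 1.06 |
| 107 | 0.95 (assumed) | 0.036 | 0.037 | 1.03 |
| 38 | 0.75 (SAP rate) | 0.113 | 0.129 | 1.15 |
| 38 | 0.50 (assumed) | 0.129 | 0.177 | 1.37 |

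**Between-imputation variance.** This dilutes the excess only a little. At P = 0.75 and N = 107 with 100 imputations, the ratio falls from 1.151 (none) to 1.127 (between-imputation variance 20% of the correct U).

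**Difference between arms.** Using the Newcombe formula in SAP 5.8.4 with both rates at 0.75:
- 38 per arm (the planned size of Cohorts 3 and 4): 0.161 becomes 0.186.
- 107 per arm: √(0.0744² + 0.0621²) = 0.097 becomes √(0.0868² + 0.0705²) = 0.112, above the 0.1 used for planning. This second case is illustrative only, because the opening of SAP 5.8.4 assigns the Mantel-Haenszel estimate to pooled cohorts and Wilson's method to single cohorts.

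**The case against.** The strongest reply is that no competent programmer would enter the success count. The method is named as Wilson and its source is cited. SAP 2.5.2 uses n for the artesunate sample size, and SAP 3.2 uses n for patients. The literal reading is also incoherent: successes vary across the 100 completed data sets while equation (2) has one fixed n, and zero successes would mean dividing by zero. SAP 5.8.4 further plans a feasibility test on blinded data at the CSR dry run. This stands as far as it goes. The excess width is conditional on coding the text as printed, and a programmer who reads n as patients gets correct limits. It does not make the printed rule right, and the dry run is not a guaranteed correction.

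Three stronger readings are tempting, and the documents do not support them.
- *That the × 100% makes P(1 − P) negative.* Since 100% equals 1, n/N × 100% is the proportion, and equation (2) plainly works on that scale.
- *That the damage is greatest at early visits.* Arithmetically the excess grows as the rate falls, and the SAP expects a median artesunate clearance time above 40 hours. But no success rate by visit is given. SAP 2.7.2.1 aims this analysis at non-malaria death and discontinuation after discharge; Table 2-4 already settles most in-hospital gaps, and those rules are applied before the multiple imputation.
- *That every treatment difference is affected.* The pooled difference is planned as Mantel-Haenszel.

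The text was converted from PDF, and equation (1) shows the same symbol twice in its numerator, so single letters deserve some caution. The lower-case n recurs consistently through U_i and equation (2), which makes a conversion artefact unlikely.

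**Conclusion.** The stated rule is wrong as written: under the SAP's own definition of n, equation (2) is not a Wilson interval. If it is followed literally, the single-arm 90% half-width is about 15% too wide at the planning rate (0.079 against 0.068, N = 107, no between-imputation variance). It is about 40% too wide at an assumed rate of 0.50, and 3–6% at assumed late rates of 0.90–0.95, the last being closest to the post-discharge visits that the analysis mainly serves. The error can only widen the limits. It reaches this sensitivity analysis and the Newcombe limits derived from it. The primary analysis, and the main 48-hour analysis by Mantel-Haenszel and Clopper-Pearson, do not use the formula. This is a minor point, worth correcting because the formula is to be hand-coded.

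**What to change.** In SAP 5.8.4, replace n by N in U_i and at every occurrence in equation (2): one place in the variance and ten in the equation as printed. Define N there as the number of FAS patients in the arm, or in the arm within the cohort for by-cohort intervals, and state that P-hat is the proportion n/N. The quantity r_m is then computed from the corrected U.

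A simple programming check is to set the between-imputation variance to zero and confirm that the coded limits equal the ordinary Wilson limits for the same counts.

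The cost is a text edit before programming, with no effect on design, data collection, sample size or any other analysis.

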5.9 Rule of exclusion criteria of analysis sets

Table 5-15 Protocol deviations and non-PD criteria leading to exclusion from analysis sets

Analysis Set	PD (Description and ID) that causes Patients to be excluded	Non-PD criteria that cause Patients to be excluded
Randomized	
 Informed Consent for study participation or parental consent not obtained and patient entered trial (INCL02) 	
 Not randomized
FAS	NA	
 Not in Randomized set Misrandomized if identified from IRT Baseline parasitaemia count is 0 or missing using local lab (central lab in case local lab is not available) No study drug taken
PPS	
 Not severe malaria for Cohort 2-5 (INCL01b) and not moderately severe malaria for Cohort 1 (INCL01a_1) Concomitant antimalarial medications (COMD01) if received before assessing the primary endpoint at 12 hours Unacceptable prior antimalarial drugs within 12 hours of screening (EXCL01.02) 	
 Not in FAS; Baseline Parasite species is other than Plasmodium falciparum OR mixed infection using local lab (central lab in case local lab is not available) Baseline Plasmodium falciparum parasite count <60000/uL or >250000/uL for cohorts 1-2 or <5000/ uL for cohorts 3-5 at using local lab (central lab in case local lab is not available)
SAF	NA	
 Not in Randomized set; No study drug taken
PK	
 Patients who received concomitant prohibited medication which may have an impact on PK exposure (COMD04) 	
 Not in SAF No evaluable pharmacokinetic parameter data Did not take at least on dose of IV study drug

6 Reference

Anne Lott & Jerome P. Reiter (2018): Wilson Confidence Intervals for Binomial Proportions With Multiple Imputation for Missing Data, *The American Statistician*, <https://doi.org/10.1080/00031305.2018.1473796>

Artesunate Package Insert. Ipca Laboratories Limited; Sep-2019.

Brand, J. P. L. (1999). Development, Implementation, and Evaluation of Multiple Imputation Strategies for the Statistical Analysis of Incomplete Data Sets. Ph.D. thesis, Erasmus University.

Brookmeyer, R. and Crowley, J. (1982) A confidence interval for the median survival time. *Biometrics*, 38, 29-41. <https://doi.org/10.2307/2530286>

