This will be an adaptive, multicenter, randomized, open label, sequential cohort study in participants aged ≥ 12 years old in Cohorts 1-2 and < 12 years old to ≥ 6 months in Cohorts 3-5 with a diagnosis of moderately severe and severe *P. falciparum* malaria (Section 16.4). This study is investigating the efficacy (parasite reduction and clinical outcome), safety, tolerability and pharmacokinetics of different injectable dose regimens of cipargamin in comparison to injectable artesunate. Cohort 1 includes only 18 participants aged ≥ 12 years old. As IV cipargamin has not yet been evaluated in patients with severe malaria, this first Cohort includes participants that are diagnosed with moderately severe malaria. Cohort 1 participants will have a minimum parasite count of 60,000 per µl and these high parasitemia levels will help to determine parasite clearance rates for the two dose regimen. In Cohorts 2-5 participants with severe malaria and a minimum parasite count of 5,000 per µl will be enrolled in an age-decreasing manner. This design aims at minimizing risks for pediatric participants < 12 years and at ensuring sufficient number of participants with severe malaria signs to evaluate their clinical improvement in the secondary endpoint. In all cohorts, participants on IV cipargamin arms will receive one daily injection of IV cipargamin over a minimum of 2 days and a maximum of 3 days; with IV artesunate as rescue medication. Participants in the IV artesunate arm will be administered a minimum of 3 doses during the first 2 days of treatment. Participants in all arms will receive Coartem bid for 3 days following IV therapy.

See sections [Section 6.1.1](#), [Section 6.1.2.1](#) and [Section 6.2.1](#) for details of each treatment arm.

Cohorts 1-2:

In Cohorts 1 and 2, 18 and 42 participants ≥ 12 years, who satisfy the inclusion/exclusion criteria will be randomized in the ratio 1:1:1 to one of three treatment arms. :

- IV cipargamin (KAE609) dose regimen 1
- IV cipargamin (KAE609) dose regimen 2
- IV artesunate

The two doses of IV cipargamin for Cohorts 1 and 2 have been selected based on the rationale described in [Section 4.2](#). The doses might be adjusted before the study start based on results obtained from the first in human (FIH) study in healthy volunteers to ensure exposure is maintained within the predicted safe and efficacious range (AUC_{0-24h} of 5-42 $\mu g \cdot hr/ml$) in the study participants.

Cohorts 3-5:

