4.1 Rationale for study design

As severe malaria is primarily a disease of young children, children down to 6 months have been included in this clinical study to obtain data in the relevant patient population. In order to ensure adequate efficacy and safety, pediatric participants will be included in an age descending manner with the youngest participant between 6 months and 2 years of age enrolled in the final cohort after IA and DMC.

As IV cipargamin has not yet been evaluated in patients with severe malaria, Cohort 1 will start with a study population, which is less severely ill and ≥ 12 years old. Participants diagnosed with moderately severe malaria and high parasitemia (60,000-250,000 parasites per μl) at baseline and without significant elevations in liver function tests (ALT and total bilirubin, see [Section 5.2](#)) will be randomized to Cohort 1. The selected inclusion criteria should limit the variability of the disease signs of participants included in Cohort 1, while allowing for efficacy assessment based upon parasite clearance and initial safety monitoring. If stopping criteria ([Table 3-1](#) in [Section 3](#)) are not met in any of the IV cipargamin arms in Cohort 1, recruitment of Cohort 2 will be initiated after LPLV (last patient last visit) of Cohort 1. In case of any efficacy/safety concerns identified in Cohort 1, PK data will be analyzed and the following actions could be taken in consultation with the data monitoring committee (DMC):

- Up to six additional participants per treatment arm may be recruited in Cohort 1 before proceeding to Cohort 2
- Dose for Cohort 2 may be modified (increased or decreased) to ensure exposure within the safe and efficacious range

In Cohort 2, participants in the same age population of ≥ 12 years diagnosed with severe malaria ([Section 16.4](#)) will be enrolled. Participants in Cohorts 2 to 5 will be enrolled with parasitemia levels of at least 5,000 parasites per μl . An interim assessment after Cohort 2 will evaluate efficacy, safety and PK results of the two IV cipargamin doses compared to IV artesunate. Based on these results, a safe and efficacious exposure range will be defined for the use in Cohorts 3-5. The dose for Cohorts 3-5 will be selected to ensure that exposure in children < 12 years of age remains within the determined safe and efficacious range.

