5.1 Inclusion criteria

Participants eligible for inclusion in this study must meet **all** of the following criteria:

1. Cohort 1: Participants aged ≥ 12 years with moderately severe malaria as defined in [Barnes et al \(2004\)](#) (prostration and/or repeated vomiting) without presence of other signs of severe malaria ([Section 16.4](#)) and with high *P. falciparum* parasitemia (60,000-250,000 parasites per μ l).

Subsequent Cohorts 2 to 5: Participants diagnosed with severe malaria as defined in [Section 16.4](#) (modified version of severe malaria criteria in [WHO 2014](#)) and *P. falciparum* parasite count of ≥ 5000 per μ l

Cohort 2: Participants aged ≥ 12 years

Cohort 3: Participants aged 6 - <12 years

Cohort 4: Participants aged 2 - < 6 years

Cohort 5: Participants aged ≥ 6 months - <2 years

2. Written informed consent form must be obtained prior to any study related procedure. If the participant is unable to read and write or otherwise incapable of signing an informed consent, then a witnessed consent according to local ethical standards is permitted (formally documented and witnessed, ideally via an independent trusted witness). Participants aged < 18 years, who are capable of providing assent, must provide assent with parental/legal guardian consent or as per local ethical guidelines. The participant or parent/legal guardian (in case of pediatric participants) is able to understand and comply with protocol requirements, instructions and protocol-stated restrictions for their child and is likely to complete the study as planned.

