Significant bleeding	Including recurrent or prolonged bleeding from nose gums or venepuncture sites; haematemesis or melaena
Shock	Compensated shock is defined as capillary refill ≥ 3 s or temperature gradient on leg (mid to proximal limb), but no hypotension. Decompensated shock is defined as systolic blood pressure < 70 mm Hg in children or < 80 mm Hg in adults with evidence of impaired perfusion (cool peripheries or prolonged capillary refill)
Hyperparasitemia	P. falciparum parasitemia > 10%
* Acidosis definition have been modified to categorize venous plasma lactate ≥ 4 mmol as acidosis .	
**Renal impairment definition have been modified to include Serum creatinine value of ≥ 3 ULN in the existing WHO definition	

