2.2 Analysis sets

Randomized set

All patients who are randomized into the study.

Full analysis set (FAS)

FAS will be comprised of all patients from Randomized set who take at least one dose of study treatment during the treatment period and whose baseline *P. Falciparum* asexual parasitaemia count is greater than 0 using local lab (central lab in case local lab assessment is not available). Following the intent-to-treat principle, patients will be analyzed according to the treatment group assigned to at randomization.

Unless otherwise specified, misrandomized patients will be excluded.

Misrandomized patients, if identified from IRT, include screen-failures, but have been randomized by the investigator before eligibility was finally assessed or mistakenly, and have not been treated. If patients were re-screened and successfully randomized, they will be included according to the treatment assigned in the last randomization.

Safety set (SAF)

Safety set includes all patients who take at least one dose of study drug during the treatment period. Patients will be analyzed according to treatment received. In particular, patient will be analyzed in the same treatment group as randomized if s/he receives at least one dose of the study medication of that group.

Per-protocol set (PPS)

Per-protocol set will be comprised of patients in FAS who did not have any important protocol deviations affecting efficacy.

Important protocol deviations and non-protocol deviations for exclusion from PPS are specified in [Table 5-15](#) and will be identified by the clinical team before the database lock.

PK analysis set

All patients who have at least one valid (i.e. not flagged for exclusion) PK concentration measurement, receive at least one dose of study drug, and do not have any protocol deviations that have an impact on PK data.

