2.5.7 Supportive analyses

The analyses specified in [Section 2.5.2](#), [Section 2.5.5](#) and [Section 2.5.6](#), will be repeated using the PPS.

Primary endpoint will be summarized descriptively by the subgroups defined in [Section 2.2.1](#). Local lab data will be used for all primary endpoint analysis for all cohorts. All the primary endpoint analysis will also be performed using central lab data for Cohorts 1 and 2.

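### SAP Table 5-15 applies Cohort 1's parasite window (60,000–250,000/µL) to Cohort 2, so eligible Cohort 2 patients drop out of the supportive per-protocol analyses

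*SAP*

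**What the plan says.** **Entry criteria.** Protocol Section 4.1 describes Cohort 1 as "Participants diagnosed with moderately severe malaria and high parasitemia (60,000-250,000 parasites per" µl). The same section says of the later cohorts: "Participants in Cohorts 2 to 5 will be enrolled with parasitemia levels of at least 5,000 parasites per" µl. Section 3 (Study design) agrees: "In Cohorts 2-5 participants with severe malaria and a minimum parasite count of 5,000 per" µl. Section 5.1 places Cohort 2 with Cohorts 3–5 under one criterion, "Subsequent Cohorts 2 to 5: Participants diagnosed with severe malaria as defined in" Section 16.4, with a count of at least 5,000/µL. None of these places gives Cohort 2 an upper limit.

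**The PPS.** SAP Section 2.2 states: "Per-protocol set will be comprised of patients in FAS who did not have any important protocol deviations affecting efficacy". It then refers to Table 5-15 for the deviations and the non-deviation criteria that lead to exclusion. The protocol's definition (Section 12.1) asks for FAS membership, the severe-malaria inclusion criterion and no deviation that affects efficacy. It names no count window.

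**The rule at issue.** The non-deviation column of Table 5-15 excludes from the PPS: "Baseline Plasmodium falciparum parasite count <60000/uL or >250000/uL for cohorts 1-2 or <5000/ uL for cohorts 3-5".

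**Where the PPS is used.** Under SAP Section 2.5.7, the primary, sensitivity and supplementary analyses "will be repeated using the PPS". Section 2.6.6 does the same for 48-hour clinical success.

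**The concern.** The exclusion rule is meant to mirror eligibility: SAP Section 2.1 speaks of removing patients with out-of-range counts. For Cohort 2 it does not. A Cohort 2 patient with 30,000/µL or 300,000/µL meets every entry criterion and has no deviation, yet is removed.

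The upper cut is awkward for a second reason. Protocol Table 16-6 lists hyperparasitemia above 10% as a sign that by itself qualifies a patient as having severe malaria. At an assumed red cell count of 3–5 million/µL, 10% is 300,000–500,000/µL. Such a patient would be excluded because of the sign that made them eligible.

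At stake is the value of the PPS as a cross-check on the FAS in patients aged 12 and over. It would be smaller, and it would hold relatively more moderately severe Cohort 1 patients and fewer severe ones than the protocol intends. A difference, or an agreement, between FAS and PPS would then be harder to interpret.

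**Working it through.** **1. Is the grouping a slip or a choice?** Four places bear on this.

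- The protocol gives the window to Cohort 1 alone (Sections 4.1 and 5.1).
- In the same PPS row of Table 5-15, the deviation column groups Cohort 2 with Cohorts 3–5 (not severe malaria) and treats Cohort 1 separately (not moderately severe malaria). The table therefore disagrees with itself.
- Neither PPS definition in the text contains a restriction narrower than eligibility.
- SAP Section 4 records no change to the protocol-specified analyses.

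All four point to a wrong cohort label.

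**2. The plan's own sample size.** Inputs from SAP Section 3.1: control rate 0.45, margin 0.10, one-sided 5%, 90% power, 13 per group. The cipargamin rate p is blacked out, so it is varied here.

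n = (1.645 + 1.282)² × [p(1 − p) + 0.45 × 0.55] / (p − 0.45 + 0.10)²

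- p = 0.85: 8.56 × 0.375 / 0.25 = 12.85, rounded up to 13
- p = 0.80: 18
- p = 0.90: 10

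The stated 13 fits a rate of about 0.85–0.86. The allowance also checks: 13 / 0.95 = 13.7, rounded up to 14. The figure of 13 is consistent with the visible inputs but cannot be fully reproduced.

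**3. Size of the PPS under the rule.** Cohort 1 has 6 per arm and Cohort 2 has 14 (SAP Section 3.2). Let f be the share of Cohort 2 outside 60,000–250,000/µL. The documents do not give f.

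PPS per arm, Cohorts 1–2 pooled = 6 + 14 × (1 − f)

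**4. Power of the planned rule at that size.** SAP Section 2.5.2 declares non-inferiority if the lower limit of the 90% Wilson uncorrected (Newcombe) interval exceeds −0.10:

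L = d − √[(p₁ − l₁)² + (u₂ − p₂)²]

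Here d = p₁ − p₂ is the observed difference, l₁ is the lower Wilson limit for cipargamin and u₂ is the upper Wilson limit for artesunate. Exact power is the sum of the binomial probabilities of all outcome pairs with L > −0.10. The control rate is 0.45, and the loss is taken as equal in both arms.

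| f | PPS per arm | p = 0.80 | p = 0.85 | p = 0.90 |
|---|---|---|---|---|
| 0% | 20 | 93% | 97% | 99% |
| 30% | 15.8, about 16 | 89% | 94% | 98% |
| 50% | 13 | 82% | 89% | 95% |
| 70% | 10.2, about 10 | 70% | 79% | 87% |

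The extremes are no loss (f = 0) and the loss of all 14 per arm (f = 100%, 42 patients over three arms). The latter leaves 6 per arm, with power of 46%, 56% and 67% for the three assumed rates.

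**5. Shift in the mix.** Cohort 1 makes up 6/20 = 30% of each arm if nobody is wrongly excluded, and 6/13 = 46% if f = 50%.

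**6. The key secondary endpoint.** This analysis pools all cohorts, with 116 randomized per arm. Losing all 14 Cohort 2 patients would leave 102. At a success rate of 0.75 in both arms, the approximate 90% half-width, 1.645 × √(2 × 0.75 × 0.25 / n), moves from 0.094 to 0.100. The effect here is small.

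**The case against.** The best case on the other side accepts the slip and disputes its consequences. Most of that case stands.

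- **The PPS does not decide anything.** A reader might infer that the PPS is the decisive check on the non-inferiority claim. The documents do not say so. Both file the PPS repeats under supportive analyses, non-inferiority is concluded on the FAS, and no rule requires the PPS to agree.
- **Dose selection.** A reader might also infer that the rule weakened the choice of the paediatric dose, since Cohorts 1–2 served that purpose. SAP Table 2-13 lists only FAS, Safety and PK outputs for the interim assessment. Protocol Section 12.7 includes all randomized Cohort 1–2 participants in it. SAP Section 1.1 records that the DMC has already endorsed doses for Cohorts 3 and 4. Protocol Section 12.1 does have PPS exclusions identified before the Cohort 1–2 lock, so PPS output may exist, but none is specified.
- **Bias between arms.** The filter uses a pre-dose value and applies alike in every arm. It shrinks and shifts the population, but does not by itself favour one arm. The SAP adjusts the parasite reduction ratio and the clearance half-life for log baseline count. Neither document shows that baseline count predicts the primary endpoint, which is a reduction relative to each patient's own baseline.
- **Exclusion without a deviation.** SAP Section 2.2 provides for non-deviation criteria, so this is not an error in itself. The error is the cohort grouping.
- **Power.** The pooled cohorts hold 20 per arm against a design need of 13, so there is room to lose patients.

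None of this makes the rule right. No other text corrects or justifies it.

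**Conclusion.** The rule is wrong as written: it applies Cohort 1's entry window to Cohort 2 and would remove eligible patients from the PPS. This follows from the text and needs no assumption.

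Its reach is limited to the supportive PPS repeats under SAP Sections 2.5.7 and 2.6.6. The FAS primary conclusion and the listed interim outputs are untouched.

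The size is conditional on two unknowns: the share of Cohort 2 outside the window, which is not given, and the cipargamin response rate, which is blacked out. At the 85% rate that the stated sample size implies, power falls materially below the 90% design target only if more than about half of Cohort 2 is excluded. At 80% it reaches 89% with 30% excluded, but a rate of 80% would not yield the planned 13 per group. This should be fixed, but the trial's main result does not depend on it.

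**What to change.** In SAP Table 5-15, change the PPS count criterion to: below 60,000/µL or above 250,000/µL for Cohort 1; below 5,000/µL for Cohorts 2–5. Do this before final database lock, so that the change cannot look driven by the results. If any Cohort 1–2 PPS output has already been produced with the present rule, re-run it.

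If the narrower window for Cohort 2 was in fact intended, state and justify it in SAP Section 4, which now reports no changes.

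The cost is one line in the SAP and one programming condition, plus the re-run if there is output to repeat.
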